If the answer to the primary question is yes, additional questions may be assessed:

Does the monotherapy (tropifexor OR licogliflozin) alone, taken once per day by participants with NASH and stage 2 or 3 fibrosis over 48 weeks, result in histologic improvement compared with placebo?

If the answer to this question is yes as well, then another question will be evaluated:

Does the combination therapy lead to more histological improvement than monotherapies?

For each primary estimand, the population, endpoint, and summary measure for the additional questions are the same as those for the primary question. Only the treatment will change accordingly. For the first additional question, the treatment of interest would be monotherapy and the control would be placebo, whereas for the second additional question, the treatment of interest would be combination therapy and the control would be monotherapy.

Intercurrent events of primary estimand will be addressed with various strategies (considering that these events occur before the histological assessments at Week 48):

- 1. Bariatric surgery: participants who have undergone bariatric surgeries during trial participation are considered as non-responders (composite variable strategy).
- 2. Use of alcohol above protocol permitted amount: the intercurrent events (overuse of alcohol) will be ignored for estimation (treatment policy strategy).
- 3. Addition or removal of any medication that may have a confounding effect on the endpoints: the treatment effect will be assessed with the intercurrent event ignored (treatment policy strategy); in the supplementary analysis, the treatment effect will be imputed as if the intercurrent event doesn't occur (hypothetical strategy)
- 4. Premature discontinuation of study treatment due to tolerability, efficacy, adherence, or adverse event: participants who discontinue the treatment after Week 24 will be asked to have their biopsies assessed at Week 48 regardless of the intercurrent event (treatment policy strategy), participants who discontinue the treatment before Week 24 will be considered as non-responders (composite variable strategy), and participants who have no biopsy extracted at Week 48 will be considered as non-responders (composite variable strategy).
- 5. Death, transplantation and other clinical outcomes: participants will be considered as non-responder (composite endpoint strategy).

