12.1 Analysis sets

Following analysis populations will be defined for the statistical analysis:

Screened analysis set (SCR) comprises of all participants who signed the informed consent.

Randomized Analysis set (RAN) comprises of all participants who received a randomization number, regardless of whether participants received study medication.

Full Analysis Set (FAS) comprises of all participants to whom study treatment has been assigned by randomization. Participants who were mis-randomized (not qualified for randomization but randomized inadvertently) and did not receive investigational medication, however, are excluded from the FAS. Efficacy analysis will be conducted on FAS. Following the intent-to-treat (ITT) principle, participants are analyzed according to the treatment they have been assigned during the randomization procedure regardless of actual treatment received and the true stratum the participant belongs to if a participant is assigned to wrong stratum during randomization.

Safety Analysis Set (SAF) includes all participants who received at least one dose of study treatment. Participants will be analyzed according to the study treatment received, where treatment received is defined as the randomized/assigned treatment if the participant took at least one dose of that treatment or the first treatment received if the randomized/assigned treatment was never received.

The number of participants in each analysis set will be presented by treatment group and overall for the screen set.

The number and percentage of participants in the randomized set who completed the study, who discontinued the study and the reason for discontinuation will be presented for each treatment group and all participants. The frequency (%) of participants with protocol deviations and criteria leading to their exclusion from each analysis set will be presented for randomized set.

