 - b. Whether the participant has resolution of NASH (absence of ballooning with no or minimal inflammation by histology) and no worsening of fibrosis at week 48 compared with baseline.
- 4. Summary measure: Odds ratio of participants achieving histological response at Week 48 for the following comparisons for each primary endpoint: combination vs. placebo, monotherapies vs. placebo, and combination vs. monotherapies.
- 5. Intercurrent events include
 - > Early discontinuation of study treatment before week 48 visit.
 - Non-histologic clinical event suggesting treatment failures (e.g bariatric surgery, liver transplant and death due to disease).
 - > Study treatment incompliance defined as relative dose intensity >1.25 or <0.75.
 - More than four weeks of cumulative exposure to any prohibited medications Section 6.2.2, alcohol usage more than what is permitted in the protocol, initiation of other T2DM or lipid lowering medication (e.g. GLP-1 modulator, statins), initiation of other treatment being evaluated or approved for NASH, or new concomitant interventions for weight control before the assessment for primary endpoint. The identification of relevant medications will be based on ATC3 and/or ATC5 codes, which will be included in analysis data set specifications. The list of concomitant interventions with significant effect for general weight loss will be determined based on blinded review of the study data.

For the intercurrent events related to the primary estimand, various strategies (such as treatment policy and composite variable) defined in ICH E9 (R1) will be utilized for the analyses. For instance, participants who discontinue the treatment after Week 24 will be asked to have their biopsies assessed at Week 48 regardless of the intercurrent event (treatment policy strategy), participants who discontinue the treatment before Week 24 will be considered as non-responders (composite variable strategy), and participants who have no biopsies extracted at Week 48 will be considered as non-responders (composite variable strategy).

Novartis	Confidential	Page 135 of 160
Amended Protocol Version 02 (Clean)		Protocol No. CLJN452D12201C

For non-intercurrent event missing data, certain multiple imputation methods will be applied to estimate the endpoints.

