12.4.3 Handling of remaining intercurrent events of primary estimand

Intercurrent events of primary estimand will be addressed with various strategies (given that these events occur before the histological assessments at Week 48):

- 1. Bariatric surgery: participants who have undergone bariatric surgeries during trial participation are considered as non-responders (composite variable strategy).
- 2. Use of alcohol above protocol permitted amount: the intercurrent events (overuse of alcohol) will be ignored for estimation (treatment policy strategy).
- 3. Addition or removal of any medication that may have a confounding effect on the endpoints: the treatment effect will be assessed with the intercurrent event ignored (treatment policy strategy). The treatment policy strategy may not be ideal if the confounding medications highly affect the endpoints. Consequently, a supplementary analysis will be conducted where the treatment effect is imputed as if the intercurrent event doesn't occur (hypothetical strategy)
- 4. Premature discontinuation of study treatment due to tolerability, efficacy, adherence, or adverse event: participants who discontinue the treatment after Week 24 will be asked to have their biopsies assessed at Week 48 regardless of the intercurrent event (treatment policy strategy), participants who discontinue the treatment before Week 24 will be considered as non-responders (composite variable strategy), and participants who have no biopsy extracted at Week 48 will be considered as non-responders (composite variable strategy).
- 5. Death, transplantation and other clinical outcomes: participants will be considered as non-responder (composite endpoint strategy).
- 6. Acute medical condition not related to the study treatment affecting the liver: participants will have their Week 48 biopsies assessed regardless of the intercurrent events (treatment policy strategy).
- 7. Acute medical condition related to the study treatment affecting the liver: participants are considered as non-responder (composite endpoint strategy).

Novartis	Confidential	Page 139 of 160
Amended Protocol Version 02 (Clean)		Protocol No. CLJN452D12201C

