12.4.4 Handling of missing values not related to intercurrent events

While not possible to confirm missing completely at random (MCAR), the histological response status from the early termination visit after at least 24 weeks of study treatment will be used for the primary analysis in case of missing primary endpoint at week 48. Participants otherwise with primary endpoint missing or any primary endpoint after intercurrent events will have the values imputed using multiple imputation (MI) methods (Rubin 1976, Rubin 1987) under a missing at random (MAR) assumption.

For multiple imputation: an arbitrary missing pattern will be assumed and a fully conditional specification (FCS) method with logistic regression will be applied. The logistic model will be used to analyze the multiple imputed datasets, and pooled results will be obtained based on Rubin's combination rules. More implementation details of the multiple imputation (MI) will be specified in the SAP.

The proportion of participants with missing primary endpoints at week 48 will be compared among the combination therapy, monotherapies and the placebo.

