 Powers of different sample sizes upper sizes upper

able 12-4 Powers of different sample sizes under equal allocation	
---	--

Sample Size					Power		
Total	LJN452	LIK066	Combo	Placebo	Cmb vs. Plc on Endpoint A	Cmb vs. Plc on Endpoint B	Cmb vs. Plc on at least one of Endpoint A and B
200	50	50	50	50	0.31	0.42	0.52
220	55	55	55	55	0.33	0.45	0.56
240	60	60	60	60	0.37	0.49	0.60
260	65	65	65	65	0.39	0.53	0.63
280	70	70	70	70	0.41	0.57	0.67
300	75	75	75	75	0.45	0.60	0.70
320	80	80	80	80	0.47	0.62	0.72
340	85	85	85	85	0.50	0.65	0.75
360	90	90	90	90	0.51	0.68	0.77
380	95	95	95	95	0.55	0.72	0.80
400	100	100	100	100	0.57	0.73	0.82

After total sample size is fixed, allocation of the four arms is assessed based on three factors:

- 1. Increasing the power of passing at least one of the combination vs. placebo tests from the two primary endpoints;
- 2. Slightly decreasing the power of passing any monotherapy vs placebo test (given that at least one of the combination vs. placebo tests have succeeded);
- 3. Constraining the size of placebo arm no larger than that of any treatment arm.

Table 12-5	Powers of passing at least one of the combination vs. placebo tests
	under various allocations of 380 participants

Sample Size				Power	
LJN452	LIK066	Combo	Placebo	Cmb vs. Plc on at least one of Endpoint A and B	
34	34	278	34	0.72	
49	49	233	49	0.80	
65	65	185	65	0.84	
80	80	140	80	0.85	
95	95	95	95	0.80	
110	110	50	110	0.62	

According to Table 12-5, allocation of 80 (LJN452), 80 (LIK066), 140 (Combo), and 80 (placebo) provides good power for passing at least one of the combination therapy vs. placebo tests from the two primary endpoints.

Power calculations were performed with simulations (n=100000) implemented in R 3.5.3, where the primary analysis in each simulated study was performed using z-tests of difference in proportions without continuity correction for simplicity.

Novartis	Confidential	Page 146 of 160
Amended Protocol Version 02 (Clean)		Protocol No. CLJN452D12201C
The missing Week 48 biopsy rate of the	e study is anticipated to	be around 20%. The missing
response data due to intercurrent event	s will be addressed wit	h intercurrent event strategies

specified in ICH E9, whereas those not related to intercurrent events will be substituted with certain multiple imputation methods. Sample size adjustment is not needed because the treatment response rates are already assumed with conservative values.

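### Protocol 12.4.4 sends endpoints after intercurrent events to multiple imputation, against its own heading and 2.1, 12.4, 12.4.3 and 12.8.1, and is the only visible rule for two listed events

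*Protocol*

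**What the plan says.** The title of Protocol 12.4.4 confines it to missing values that have nothing to do with intercurrent events. Its text goes further: "Participants otherwise with primary endpoint missing or any primary endpoint after intercurrent events will have the values imputed using multiple imputation (MI) methods", under a missing-at-random assumption.

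Protocol 2.1 and 12.4.3 give a numbered list of events, each with a strategy. For confounding medication (item 3), "the treatment effect will be assessed with the intercurrent event ignored (treatment policy strategy"; in addition, "a supplementary analysis will be conducted where the treatment effect is imputed as if the intercurrent event doesn't occur (hypothetical strategy". For early stopping (item 4), "participants who discontinue the treatment before Week 24 will be considered as non-responders (composite variable strategy". Nowhere in these lists is imputation the primary rule.

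The scope of multiple imputation is stated twice more. Protocol 12.4: "For non-intercurrent event missing data, certain multiple imputation methods will be applied". Protocol 12.8.1, on missing responses: "those not related to intercurrent events will be substituted with certain multiple imputation methods".

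Protocol 12.4 also lists intercurrent events. One is "Study treatment incompliance defined as relative dose intensity >1.25 or <0.75". Another is the start of a new intervention for weight control.

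**The concern.** The primary test has two incompatible rules for the same participants. Under 12.4.4 an observed Week 48 biopsy taken after an intercurrent event is set aside and replaced by an imputed value, and an assigned non-response is overwritten in the same way. That estimates what would have happened without the event. It is a hypothetical estimand, whereas 2.1 declares a mix of treatment-policy and composite strategies.

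The clause probably survives from an older design. SAP 2.5.3, dated December 2019 and written for three arms without placebo, contains almost the same sentence. There it fits, because SAP 2.5 adopts a while-on-treatment and hypothetical approach. Carry-over is an inference, but a natural one.

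For two events the clause is also the only rule a reader can find, so it cannot be dismissed as a stray phrase, and deleting it alone would leave those events with no rule.

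**Working it through.** **Passages side by side**

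| Event | 2.1 and 12.4.3 | 12.4.4 read literally |
|---|---|---|
| Bariatric surgery | non-response | imputed |
| Alcohol above the limit | observed biopsy | imputed |
| Confounding medication | observed biopsy; imputation supplementary | imputed |
| Stopping before Week 24 | non-response | imputed |
| Stopping after Week 24, Week 48 biopsy done | observed biopsy | imputed |
| Death, transplantation | non-response | imputed |
| Acute liver condition, unrelated to treatment | observed biopsy | imputed |
| Acute liver condition, related to treatment | non-response | imputed |
| Relative dose intensity above 1.25 or below 0.75, still on treatment | no rule | imputed |
| New weight-control intervention, neither surgery nor medication | no rule | imputed |

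Item 4 mentions adherence only as a reason for stopping treatment, so it does not reach the ninth row.

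**Inputs for the size**

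- Table 12-3: 35% versus 20% (fibrosis endpoint) and 25% versus 10% (NASH resolution), combination versus placebo.
- Section 12.8.1: participant-level correlation 0.5; 140 versus 80 participants; z-test without continuity correction; about 20% of Week 48 biopsies missing.
- Section 12.4.2: two-sided 5% split evenly, so two-sided 2.5% per endpoint.
- Assumed: missingness balanced between arms, events independent of outcome, and 10%, 20% or 30% of the remaining biopsies following an event.

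**Step 1: reproduce the plan.** With z = (p1 − p2) / √[p1(1 − p1)/n1 + p2(1 − p2)/n2], simulated power for at least one endpoint is 0.80 at 95 per arm (Table 12-4: 0.80) and 0.85 at 140 versus 80 (Table 12-5: 0.85).

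**Step 2: 20% missing.** Observed: 140 × 0.8 = 112 and 80 × 0.8 = 64.

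- All missing counted as non-response: rates become 0.35 × 0.8 = 0.28 versus 0.20 × 0.8 = 0.16, and 0.25 × 0.8 = 0.20 versus 0.10 × 0.8 = 0.08, with 140 and 80 as denominators. Power 0.74.
- All missing imputed, 50 imputations, Rubin's rules, response probability drawn from Beta(x + 0.5, n − x + 0.5), no covariates. Drawn separately by arm (treatment in the imputer): about 0.76. Drawn once for combination and placebo together (treatment left out): about 0.54.

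The second imputer matters because SAP 5.4.2, and item 4.9 of SAP section 4, exclude treatment from the imputation model. Imputed values then carry no expected arm difference, so the difference of 0.15 shrinks to 0.15 × 0.8 = 0.12, and imputation variance is added on top.

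**Step 3: add the literal clause.**

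| Share of remaining biopsies discarded | Biopsies discarded (combination + placebo) | Left | Power, treatment in imputer | Power, treatment left out |
|---|---|---|---|---|
| 0% | 0 | 112 / 64 | 0.76 | 0.54 |
| 10% | 11 + 6 | 101 / 58 | 0.71 | 0.38 |
| 20% | 22 + 13 | 90 / 51 | 0.66 | 0.20 |
| 30% | 34 + 19 | 78 / 45 | 0.60 | 0.08 |

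**The case against.** The best defence is that the intention is plain. The heading of 12.4.4, together with 2.1, 12.4, 12.4.3 and 12.8.1, points one way, against one leftover clause. Section 12.4.4 defers imputation detail to the SAP. The SAP available predates both amendments and says it may be revised, so a later version may already settle the matter. For the events that 12.4.3 covers, this is a conflict of wording whose answer can be inferred.

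That much stands. It does not remove the point. The clause is an operative sentence in the primary analysis, the only SAP in hand repeats it, and no other passage answers the two uncovered events.

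Four stronger readings are tempting and are not supported:

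- A reader might take the low power figures as this trial's power. They rest on assumed event shares and a simplified imputer without covariates, and the SAP's exclusion of treatment was written for the earlier design.
- A reader might instead conclude that non-response or imputation makes little difference when missingness is balanced (0.74 against 0.76). That holds only with treatment in the imputer; without it the comparison is 0.74 against 0.54.
- A reader might hold that 12.1 already dictates treatment policy for non-compliance: "Following the intent-to-treat (ITT) principle, participants are analyzed according to the treatment they have been assigned during the randomization procedure". That sentence fixes the arm in which a participant is analysed, not how outcomes after non-compliance are used.
- A reader might see a second contradiction in the use of an early-termination biopsy, because item 4 makes participants without a Week 48 biopsy non-responders. Item 4 covers four named reasons for stopping, and section 8.3.1.8, to which Table 8-1 refers, is not in the text available. This is only something to check there.

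**Conclusion.** The contradiction is real and lies in current protocol text. As written, 12.4.4 replaces observed biopsies and assigned non-responses that 2.1 and 12.4.3 preserve, and so changes the primary estimand. Two intercurrent events named in 12.4 have no strategy other than this clause. It must be corrected before unblinding, because two available rules for the primary test leave room to choose between them afterwards.

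The size cannot be fixed from the documents, which give no event shares. On the stated assumptions, the literal clause lowers power from about 0.76 to between 0.71 and 0.60 with treatment in the imputer, or from about 0.54 to between 0.38 and 0.08 without it. Events are taken as independent of outcome, so these figures reflect discarded information and, with treatment left out, the shrinkage built into that imputer. If events relate to outcome, the estimate shifts as well, in a direction the documents do not reveal. The planned rates are read as rates among participants with a biopsy; if they already allow for non-response, the 0.74 does not apply.

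**What to change.** 1. In Protocol 12.4.4, delete the part of the sentence that concerns endpoints after intercurrent events, so that imputation covers only missing Week 48 endpoints not already handled by 12.4.3.
2. In the same edit, state in 2.1 and 12.4.3 a strategy for non-compliance by relative dose intensity in participants who stay on treatment, and for new weight-control interventions other than surgery or medication. Treatment policy would be consistent with items 2, 3 and 6, but the documents do not dictate it.
3. Align SAP 2.5 and 2.5.3 with the result before unblinding, keeping hypothetical imputation only as the supplementary analysis in item 3.

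The cost is a few sentences in the two documents. No new data or participants are needed.

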12.4.5 Sensitivity analyses for primary endpoint(s)/estimand(s)

Any sensitivity analysis of the primary efficacy estimands will be described in the SAP.

12.5 Analysis of secondary endpoints

Summary tables of descriptive statistics will be presented by treatment group, and by scheduled visit where applicable, for secondary endpoints. Counts and percentages will be presented for categorical variables and the arithmetic mean, standard deviation, minimum, maximum, median and first and third quartile will be presented for continuous variables.

12.5.1 Efficacy

endpoint(s)

Secondary efficacy endpoints will be analyzed in the FAS and planned analyses are outlined in Table 12-1 below:

Novartis ---- Confidential

Table 12-1Planned Analyses	
Endpoints	Analysis
Key secondary endpoint: whether the participant achieves resolution of NASH and no worsening of fibrosis OR Improvement in fibrosis by at least one stage without worsening of NASH at Week 48 compared with baseline.	Same statistical methods as for one branch of the primary analysis with overall Type I error rate controlled at two sided 0.05 level.
Whether (yes or no) the participant has at least one stage improvement in fibrosis at week 48 compared with baseline	Same statistical methods as for the key secondary endpoint analysis with neither hypothesis tests nor p-values.
Whether (yes or no) the participant has at least two stage improvement in fibrosis stage and no worsening of NASH at week 48 compared with baseline	Same statistical methods as for the primary analysis with neither hypothesis tests nor p-values.
Change in liver fat content based on MRI - PDFF (in 40% of participants) over time up to Week 48 compared with baseline	Descriptive statistics, adjusted mean and mean differences of treatment of interest vs. alternative treatment with 95% CI by scheduled visits based on repeated measurement analysis of covariance (ANCOVA) model will be presented.
Whether (yes or no) the participant has 5% or more reduction in body weight at Week 48 compared to baseline	Number and percentage of participants with 5% or more reduction in body weight. Difference in percentages between treatment of interest and alternative treatment along with 95% CI calculated based asymptotic normal distribution of difference in proportions will be presented. CMH test stratified with baseline T2DM status will be performed to estimate odds ratio (95% CI) between treatment of interest and alternative treatment.
Change in ALT and AST over time up to Week 48 compared with Baseline	The mixed model of repeated measurement will be fitted to changes from baseline in these endpoints over time. The point estimate and the associated 95% CI of the change from each treatment at each visit will be presented.
Change in GGT over time up to Week 48 compared with Baseline	The mixed model of repeated measurement will be fitted to changes from baseline in GGT over time. The point estimate and the associated 95% CI of the change from each treatment at each visit will be presented.

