12.4.2 Statistical model, hypothesis, and method of analysis

The main goal of the study is to reveal the efficacy of the combination therapy (tropifexor + licogliflozin) compared with placebo in the two primary endpoints, so the two tests of combination therapy vs. placebo (one for each endpoint) will be conducted first. The study will be considered successful if at least one of these two tests passes with statistical significance. An overall two-sided 5% (one-sided 2.5%) alpha is adopted to the study and is splitted evenly to the two primary endpoints. In addition to the comparison between combination therapy and placebo, another four pairwise comparisons may be evaluated for each primary endpoint, rendering a total of ten ([1+4]*2=10) potential comparisons. Each primary endpoint will have its own branch of tests and may pass its alpha to the other branch from its last two tests. Under each branch, the two monotherapies (LJN452 and LIK066) will be compared with placebo after the combination treatment shows superiority over placebo with significant evidence. If one of the monotherapy vs. placebo tests succeeds, then it will pass its alpha to the corresponding combination vs. monotherapy test. An alpha recycling graph (Bretz et al 2009) is presented in Figure 12-1 below to illustrate the test relationship.

Figure 12-1 An alpha recycling graph

Within each primary endpoint branch, five comparisons may be evaluated in the following levels:

- Combination vs. placebo
- Tropifexor (LJN452) vs. placebo; licogliflozin (LIK066) vs. placebo
- Combination vs. tropifexor (LJN452);
- Combination vs. licogliflozin (LIK066);

Since there are two primary endpoints, a total of ten comparisons may be tested.

The comparisons are based on the four arms of the study: one combination therapy arm, two monotherapy arms and one placebo arm. The proportions of histological responders in these four arms are assumed following binomial distributions (n, p). The sampling distribution of the difference $\hat{p}_{m_{_i}} - \hat{p}_{m_{_j}}$ will be asymptotically normal with mean $p_{m_{_i}} - p_{m_{_j}}$ and variance $\frac{p_{m_i}(1-p_{m_i})}{n_{m_i}} + \frac{p_{m_j}(1-p_{m_j})}{n_{m_j}}$, where *m* is the index of the primary endpoint (m = A if the

Novartis	Confidential
Amended Protocol Version 02 (Clean)	

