Combination vs. placebo (test 1, k = 1, i = Cmb, j = Plc)

Tropifexor (LJN452) vs. placebo (test 2, k = 2, i = LJN, j = Plc); licogliflozin (LIK066) vs. placebo (test3, k = 3, i = LIK, j = Plc)

Combination vs. tropifexor (LJN452) (test 4, k = 4, i = Cmb, j = LJN); combination vs. licogliflozin (LIK066) (test 5, k = 5, i = Cmb, j = LIK)

There are ten potential tests to be performed for the two primary endpoints (five for each primary endpoint), and it is important to control the overall Type I error rate for these tests. The alpha recycling graph presented in Figure 12-1 shows how alpha transfers among them. If the data fails to reject the null hypothesis of a test, then the alpha of that test will not be passed to others. This restriction ensures the control of overall Type I error rate. Again, for the primary

Confidential

Amended Protocol Version 02 (Clean) Protocol No. CLJN452D12201C endpoints, the overall alpha is set at two-sided 5%. A logistic regression model with the logit of probability for histological response as the dependent variable, treatment groups as the main effect, baseline fibrosis stage and T2DM (No/Yes) as explanatory variables, and the baseline BMI as a covariate will be utilized to test the hypotheses at each step. While this model will be the typical logistic regression in most cases, it should be set as the Firth logistic regression if some arm (such as the placebo) has a low response rate, as the Firth method returns less biased results for data with rare events. The null hypothesis of *k*th test, if executed, will be rejected if the p-value for the coefficient of treatment effect in the *k*th comparison is less than or equals to its corresponding alpha. If no alpha is passed to a specific comparison, then its corresponding test will not be performed and p-value will not be calculated. More statistical specifications of the model will be described in the statistical analysis plan (SAP).

The number and percentages of histological responders at week 48 in FAS will be summarized by treatment groups. The difference between the treatment of interest and the alternative treatment will be presented along with 95% confidence interval calculated based on the normal approximation for distribution of the difference between two binomial random variables.

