12.8.2 Secondary endpoint(s)

The tests of the key secondary endpoint are not used for sample size calculation. These tests are similar to the five tests of each primary endpoint and will be performed after the tests of primary endpoints succeed.

13 Ethical considerations and administrative procedures

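### The key secondary composite is tested at a two-sided 0.05 that the primary alpha scheme does not fund, behind a gate that is not defined; if combination-vs-placebo wins open it, strong family-wise control can fail (about 6–8%)

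*Protocol*

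**What the plan says.** Protocol Section 12.4.2 sets the error budget: "An overall two-sided 5% (one-sided 2.5%) alpha is adopted to the study and is splitted evenly to the two primary endpoints". On recycling it says "Each primary endpoint will have its own branch of tests and may pass its alpha to the other branch from its last two tests", and on the size of the family "Since there are two primary endpoints, a total of ten comparisons may be tested". Alpha leaves a test only on rejection: "If the data fails to reject the null hypothesis of a test, then the alpha of that test will not be passed to others". No route from these ten tests to any other endpoint is described.

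Table 12-1 (Section 12.5.1) then lists the composite (NASH resolution without worse fibrosis, or fibrosis improvement without worse NASH) as key secondary, with this analysis: "Same statistical methods as for one branch of the primary analysis with overall Type I error rate controlled at two sided 0.05 level". One branch is five tests. The two other histological secondaries in that table have no hypothesis tests and no p-values.

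The only gate is in Section 12.8.2: the composite tests "will be performed after the tests of primary endpoints succeed". The nearest definition of success is in Section 12.4.2, and it concerns the study as a whole: "The study will be considered successful if at least one of these two tests passes with statistical significance".

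The SAP is dated 09-Dec-2019 and describes the three-arm, 210-patient, one-sided design. Its Sections 2.6 and 2.6.2 put the key secondary tests in one hierarchical chain of six hypotheses with overall error 0.05, opened only when both primary nulls are rejected. That covers different endpoints, arms and error level, so it does not settle the question for the four-arm design.

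**The concern.** A hierarchical plan keeps its error rate only if every formal test runs on alpha that belongs to it or has been released by a rejected test. Here 0.025 + 0.025 = 0.05 is already used in the primary branches. A combination-vs-placebo win passes its 0.025 down its own branch to the monotherapy tests, so that alpha is still at work when the composite branch starts with another 0.05. The monotherapy and combination-vs-monotherapy questions are then asked again on the composite with alpha that no primary test gave up.

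At stake is what a positive composite result can support. The protocol describes the study as enabling Phase 3 and chose two-sided 5% on health authority advice. The composite is the one secondary endpoint singled out for formal testing. As written, either it falls outside the study's error control or its gate almost never opens.

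**Working it through.** **Inputs.** Alpha 0.025 per primary endpoint, and two-sided 0.05 for the composite branch (Sections 12.4.2 and 12.5.1). Arms 140/80/80/80. Placebo 20% on endpoint A (fibrosis) and 10% on endpoint B (NASH resolution). Planned combination 35%/25% and monotherapies 30%/20% (Table 12-3). Participant-level correlation 0.5 (Section 12.8.1). The composite is A or B.

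**1. The plan's own power.** Simulating z = (p̂ᵢ − p̂ⱼ) / √[p̂ᵢ(1−p̂ᵢ)/nᵢ + p̂ⱼ(1−p̂ⱼ)/nⱼ] at two-sided 0.025 per endpoint gives 0.547 / 0.719 / 0.802 (A / B / at least one) with 95 per arm. Table 12-4 states 0.55 / 0.72 / 0.80. At 140/80/80/80 it gives 0.851, against 0.85 in Table 12-5. Using 0.05 per endpoint instead gives 0.65 / 0.79 / 0.87, which does not match. So the stated power already spends 0.025 + 0.025 = 0.05.

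**2. Assumed graph.** Figure 12-1 is not shown. Following the text, each combination-vs-placebo test passes half its alpha to each monotherapy-vs-placebo test. Each of those passes everything to its combination-vs-monotherapy test, which passes everything to the other branch. The even split is an assumption. The composite branch has the same shape, starting at 0.05.

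**3. Limiting case.** Let the combination effect be overwhelming and the monotherapies equal placebo.
- Primary graph: four null tests at 0.025/2 = 0.0125, nominal sum 4 × 0.0125 = 0.05.
- Composite branch: two null tests at 0.05/2 = 0.025, nominal sum 2 × 0.025 = 0.05.
- Total alpha in play: 0.10. Allowing for correlation (A with B 0.50, composite with A 0.94, composite with B 0.63), the error is 4.5% from the primary graph alone and 6.7% with the composite added.

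**4. Finite-sample simulation.** Chance of at least one false claim at correlation 0.5. Ranges run from pooled to unpooled z unless marked.

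| True rates (A/B), placebo 20/10 | Primary graph alone | Plus composite, one win opens it | Plus composite, both wins needed |
|---|---|---|---|
| All arms equal placebo | 4.7–5.3% | 4.7–5.3% | 4.7–5.3% |
| Combination 35/25, monotherapies = placebo | 2.6% (unpooled) | 3.9–4.4% | 3.8% (unpooled) |
| Combination 40/10, monotherapies = placebo | 4.5% (unpooled) | 5.7–6.4% | 4.5% (unpooled) |
| Combination 50/40, monotherapies = placebo | 4.0–4.4% | 6.3–6.9% | 6.1–6.8% |
| All active arms 35/25 | not tabulated | 1.6–1.9% | not tabulated |
| All active arms 50/40 | 3.6–4.1% | 6.6–7.5% | 6.5–7.2% |
| All active arms 60/50 | 4.5% (pooled) | 7.5% (pooled) to about 8% | close to the one-win figure |

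Repeat runs differ by a few tenths of a point. With correlation 0.3, all active arms at 50/40 gives 7.2–8.0%. The unpooled test is itself slightly liberal (5.3% under the global null), so the lower ends are the cleaner measure of the excess.

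**5. How often each gate opens at Table 12-3 rates.** At least one combination-vs-placebo win: 80–85% of trials. Both: 47–54%. All ten primary tests: 55 of 2,000,000 = 0.0000275, about 0.003%. The last figure is so small because each combination-vs-monotherapy test is rejected in only about 0.04% (A) or 0.11% (B) of trials.

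**The case against.** **The gate wording is ambiguous, not plainly loose.** The at-least-one rule defines study success; it does not say when composite testing starts. Section 12.8.2 uses an unqualified plural, and the older SAP required every primary null to be rejected. A reader might infer that the plan clearly starts composite testing after a single win. The documents do not say that, so the inflation is conditional on how the gate is read. This stands.

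**A reader might infer that the protocol's claim of 5% is false.** The text does not support that either. Section 12.4.2 ties the figure to the primary endpoints ("endpoints, the overall alpha is set at two-sided 5" percent), and Table 12-1 can be read as 5% within the composite's own family. On that reading nothing is breached inside the family, but a composite claim lies outside the study-wise 5%, and the protocol does not say so.

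**The excess needs particular truths.** It is absent under the global null. It is below 5% with the combination at planned rates and null monotherapies, and under 2% with all active arms at the planned combination rates. The clearest excess comes from effects well above Table 12-3. This also stands, but strong control means control under every configuration. One nearer to plan (combination 40%/10%, monotherapies null) already exceeds 5% if a single win opens the gate.

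**A reader might infer that under the all-ten gate the endpoint can never be tested.** That goes too far. With a combination at 70%/60% and monotherapies at 45%/35%, all ten tests are rejected in about 70% of trials. Practically never holds at the planned rates.

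**Figure 12-1 might contain an edge to the composite.** This cannot be excluded. The text, however, counts ten tests and describes passing only between the two primary branches.

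**Conclusion.** The point holds in conditional form. The composite's 0.05 is not funded by the scheme the text describes, and the condition that opens it is not defined.

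- If one or both combination-vs-placebo wins open it, strong family-wise control over primary plus key secondary fails. The error is about 6–7% with a 50%/40% combination and null monotherapies, 6.6–7.5% with all active arms at 50%/40%, and up to about 8% at 60%/50%.
- If all ten primary tests must succeed, error is controlled but the test is practically unreachable at planned rates (about 0.003% or less).
- If a separate family is meant, the composite carries no study-wise protection.

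The sizes rest on the assumed graph with even splits, correlation 0.5, simple z-tests in place of the planned logistic model, and complete data. The primary tests and the study's success criterion are unaffected. It should be corrected before unblinding, because the choice of gate decides whether a composite p-value is confirmatory.

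**What to change.** Remove the separate 0.05 from Table 12-1 and state the gate exactly, in one of two ways.

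1. **Test it inside the graph.** Make the five composite tests nodes of Figure 12-1 that use only alpha released by rejected primary nodes, with the weights written down. For example, a stated fraction of a branch's 0.025 could go to the composite combination-vs-placebo test once that branch's combination-vs-placebo test is rejected. Where the edges start matters: if alpha is released only from the combination-vs-monotherapy tests, the composite is again almost never reached at Table 12-3 rates.
2. **Do not test it.** Report the composite with confidence intervals and no p-values, as for the other two histological secondaries in Table 12-1.

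If a separate family is really intended, say that composite claims are not covered by the study-wise 5%.

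In each case align Section 12.8.2, the graph and the SAP, which must in any event be rewritten for the four-arm design. The cost is a short text edit. Option 1 also takes some power from the tests that now share alpha, chiefly the monotherapy comparisons; this loss has not been computed and should be simulated when the weights are chosen.
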